J On a dosing day, blood draws should be completed on the same day of IP administration. The + 7 days after each dose PK / PD sample and coagulation blood sample can occur following IP administration at or after any visit following Month 6 Visit ([Section 1.3.3](#)). If Screening is extended up to 60 days (with permission from the sponsor), there is no need to repeat the hematology / coagulation / biochemistry assessments. If the subject is not eligible for enrollment after 60 days, they will be screen failed (or rescreened with permission from the sponsor). Collection of blood for hematology and / or biochemistry at Visit Months 4 and 10, if feasible, and provided that the cumulative blood volume to be drawn per visit does not exceed the total volume per visit as provided in the Laboratory Manual.

K If clinical confirmation of C1-INH HAE in the medical records is not available, a blood sample to confirm the HAE disease will be collected at Screening.

L An individual acute treatment plan will be developed by the investigator to ensure that participating subjects are capable of managing their HAE attacks during the study. The action plan will be reviewed with subjects.

M Subjects may use the on-demand medication of their choice to treat HAE attacks experienced during the study if that medication is used according to the product label.

N Subjects will be administered a 100 mg dose of CSL312 via SC injection on the first day of the Treatment Period. The parent / caregiver will be trained in IP administration at Visit Day 1 (further training may be provided at any subsequent visits as needed). At the discretion of the investigator, the investigational product may be administered by a trained caregiver at home (including on-site visit days) after completing training and after the first dose is administered at the study site under medical supervision. Subjects 2 to 5 years of age will receive 100 mg CSL312 every 2 months. During administration of CSL312, any device malfunctions should be reported as a suspected Product Technical Complaint. Refer to the Site Investigational Product Manual for additional information.

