**1.3.3. Schedule of Assessments - Post-dose Pharmacokinetic and Coagulation Sampling (Treatment Period)**

Study Period	Treatment Period
Sampling Time	+7 days (± 1 days) after Month 6 administration or thereafter A
Pharmacokinetics / pharmacodynamics	X
Coagulation blood sample	X

A Post-dose blood draws to occur after the administration of CSL312 at Visit Month 6 or at site visits thereafter.

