**6.8. Investigational Product Compliance**

The investigational product will be administered to the subjects at the site directly from the investigator (or delegate), under medical supervision. The date and time of each dose administered at the site will be recorded in the source documents. The dose of investigational product and the subject's identification will be confirmed at the time of dosing by a member of the study site staff other than the person administering the investigational product.

At the discretion of the investigator, the investigational product may be administered by a trained caregiver at home (including on-site visit days) after completing training and after the first dose is administered at the study site under medical supervision. Compliance with investigational product will be assessed at each visit. For investigational product that is administered at the site, treatment compliance will be assessed by using the administration details documented in the source documents and relevant form. For investigational product that is administered at the subject's home, compliance will be assessed by review of completed subject dosing form and direct questioning during the following site visit, documented in the source documents. Deviation(s) from the prescribed dosage regimen should be recorded.

A record of the quantity of investigational product dispensed to and administered by each subject must be maintained and reconciled with study intervention and compliance records. Intervention start and stop dates, including dates for investigational product delays and / or dose reductions, will also be recorded.

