### **9.2. Sample Size Determination**

Not applicable; this study will enroll a prespecified number of subjects as agreed with health authorities.

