#### 9.4.4. Pharmacokinetics Analyses

The PK parameters after SC administration of CSL312 at steady state are primary endpoints in this study. The PK analysis will be performed using the PK Analysis Set.

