##### 9.4.4.1. Analysis of Primary Pharmacokinetic Endpoint

Plasma concentrations of CSL312 will be listed by individual subjects and will be summarized by nominal time points and by dosing regimen (ie, 100 mg Q2M, 100 mg Q1M) using the PK Analysis Set. Plasma concentrations will be summarized with descriptive statistics: n, mean, SD, percent coefficient of variation (CV%), median, minimum, maximum, first and third quartiles for continuous variables, and geometric mean and its respective 90% CI.

PK parameters will be derived using noncompartmental PK analyses and will be summarized descriptively by dosing regimen (ie, 100 mg Q2M, 100 mg Q1M). PK parameters will include maximum plasma concentration ( $C_{\max}$ ), trough plasma concentration ( $C_{\text{trough}}$ ), and time to reach maximum plasma concentration ( $T_{\max}$ ). The following descriptive statistics will be presented for all PK parameters, except for  $T_{\max}$ : n, mean, SD, CV%, median, geometric

mean, geometric CV%, minimum, and maximum. For  $T_{max}$ , n, median, minimum, and maximum will be provided.

Additional information on the analyses of PK parameters will be provided in the SAP.

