This SAP complies with the International Council for Harmonisation (ICH) E9 'Statistical Principles for Clinical Trials' and E9(R1) 'Statistical Principles for Clinical Trials: Addendum on Estimands and Sensitivity Analysis in Clinical Trials', and is based upon the following study documents:

- Clinical Study Protocol Amendment 3, dated 9 January 2025
- electronic Case Report Form (eCRF), Version dated 30 Jan 2025

Population pharmacokinetic (PK) analyses are described within the modeling and simulation analysis plan (MSAP) and reported separately.

Mock tables, listings, and figures (TLF) shells are provided in a separate supporting document.

All decisions regarding the final analysis of the study results, as defined in this SAP, have been made before database lock (DBL) of the study data. Deviations from the planned analyses in this SAP will be detailed in the CSR.

3 Study Design

This is a multicenter, open-label, phase 3b pediatric study designed to investigate the safety, PK / pharmacodynamics (PD), and efficacy of subcutaneous (SC) administered CSL312 in the prophylactic treatment of hereditary angioedema (HAE) in children 2 to 11 years of age. The study schematic is shown in [Figure 1](#). The study will enroll a target sample size of approximately 20 subjects to ensure that at least 15 subjects complete 12 months of treatment.

[figure not shown]
The following subjects will be eligible to participate in this study if they meet all eligibility criteria:

- CSL312-naïve pediatric subjects with C1-esterase inhibitor (C1-INH) HAE type 1 or 2

CSL312 will be administered SC at a dose of 100 mg once monthly (Q1M; subjects 6 to 11 years of age) or every 2 months (Q2M; subjects 2 to 5 years of age) for at least 12 months.

The study will consist of a Screening Period, an open-label Treatment Period, and Follow-up Period. The Follow-up Visit takes place 3 months after last dose of CSL312. Subjects who complete the study have the option to continue treatment with CSL312 or another prophylactic treatment without a scheduled follow-up. Subjects who do not choose the post-study access program or another prophylactic treatment will complete the Follow-up Visit as mandated in this study.

Figure 1 Overall Study Schema

C1-INH = C1-esterase inhibitor; HAE = hereditary angioedema.

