11.2 Deriving and Summarizing Pharmacokinetic Parameters

PK parameters will be derived using non-compartmental PK analyses and will be summarized descriptively by dosing regimen (i.e., 100 mg Q2M, 100 mg Q1M).

The following descriptive statistics will be presented for all PK parameters, except for T_{\max} : number of observations (for definition see [Section 11.1](#)), mean, SD, CV%, median, minimum, and maximum, geometric mean, geometric CV% (for definition see [Section 11.1](#)). For T_{\max} , number of observations, median, minimum, and maximum will be provided.

By-subject listings will be provided for the PK parameters.

12 Pharmacodynamic and Biomarkers Analyses

All analyses in this section will be based on the PD Analysis Set.

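### Noncompartmental Tmax is set by the single +7-day draw, Cmax is in effect the day-7 concentration, and dosing-day trough draws are not required to be pre-dose

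*Protocol*

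**What the plan says.** Protocol 9.4.4 states: "The PK parameters after SC administration of CSL312 at steady state are primary endpoints in this study". Protocol Table 2 and SAP Table 1 name them as Cmax, Ctrough and Tmax, with Tmax summarized by median, minimum and maximum. The method is noncompartmental in both documents: "PK parameters will be derived using noncompartmental PK analyses and will be summarized descriptively by dosing regimen" (Protocol 9.4.4.1) and "PK parameters will be derived using non-compartmental PK analyses and will be summarized descriptively by dosing regimen" (SAP 11.2).

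Protocol 1.3.3 has one sampling column, at plus "7 days (± 1 days) after Month 6 administration or thereafter". All other PK draws are at visits: Day 1 and Months 4, 6 and 12 for ages 2 to 5 (Q2M, Section 1.3.1), and Day 1 and Months 3, 6, 9 and 12 for ages 6 to 11 (Q1M, Section 1.3.2). No dose is given at Month 12 (End of Treatment).

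On order within a dosing day, Section 1.3.1 footnote J says only: "On a dosing day, blood draws should be completed on the same day of IP administration". Section 1.3.2 footnote K and Section 8.5 set the same same-day rule. Section 6.8 adds that, at the investigator's discretion, "the investigational product may be administered by a trained caregiver at home (including on-site visit days"), once training is complete and the first dose has been given on site.

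SAP Section 2 notes: "Population pharmacokinetic (PK) analyses are described within the modeling and simulation analysis plan (MSAP) and reported separately". That model is not the stated source of the primary parameters.

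**The concern.** A noncompartmental Tmax is read off the sampling times. With one post-dose time there is nothing to choose between, so the reported median and range would describe the visit window, not the drug. The value called Cmax is whatever the concentration happens to be about a week after dosing. The dose rationale (Protocol 4.3) rests on steady-state exposure similar to adults, so a reader comparing paediatric with adult Cmax or Tmax could be misled by the labels.

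Ctrough has a different weakness. A child dosed at home in the morning and bled in clinic that afternoon has followed every rule, yet the sample is on the rising limb of the new dose. The proportional error is largest where the trough is lowest, which is the Q2M group aged 2 to 5.

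**Working it through.** **No planned figure to reproduce.** Protocol 9.2 reads "Not applicable; this study will enroll a prespecified number of subjects as agreed with health authorities", and nothing below depends on sample size.

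**Step 1: samples per dosing interval, from Sections 1.3.1 to 1.3.3.**
- Q2M: Month 6 dose, same-day draw and possibly +7 d; Month 8 dose, +7 d only; Month 10 dose, +7 d and End of Treatment (about 60 d).
- Q1M: Month 6 or Month 9 dose, same-day draw and +7 d. End of Treatment is about 30 d after the Month 11 dose.

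No interval has two different post-dose times near the peak. Footnotes J and K refer to a +7-day sample following every dose, whereas Section 1.3.3 has a single column. The two need reconciling, but repeated day-7 draws would still be at one time point.

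**Step 2: Tmax.** The window is 7 − 1 = 6 to 7 + 1 = 8 days. SAP 11.1 sets pre-dose time to 0, so the only other likely outcome is Tmax = 0, when the pre-dose value exceeds the day-7 value. In a simulation (20,000 draws per case, 19-day half-life, assumed 15% residual error, true Tmax from 2 to 12 d), the median noncompartmental Tmax was 6.7 to 7.0 d, and every non-zero value lay in 6.0 to 8.0 d. Tmax = 0 occurred in Q1M in at most 0.1% of cases for true Tmax up to 7 d, 3.6% at 10 d and 23% at 12 d. In Q2M it was about 0%.

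**Step 3: size of the Cmax and Ctrough errors.** Inputs:
- half-life 19 d (Protocol 2.1.1.2.1, healthy adult males; assumed for children);
- ke = ln 2 / 19 = 0.0365 per day;
- dosing interval τ = 30 or 60 d;
- ka = 0.1 to 0.8 per day (assumed; the documents give none).

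One-compartment, first-order absorption, at steady state, up to a constant:

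C(t) = exp(−ke·t)/(1 − exp(−ke·τ)) − exp(−ka·t)/(1 − exp(−ka·τ))

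Tmax = ln[ka(1 − exp(−ke·τ)) / (ke(1 − exp(−ka·τ)))] / (ka − ke)

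| Regimen | ka (/d) | True Tmax (d) | C(7 d)/Cmax | C(4 h)/Ctrough |
|---|---|---|---|---|
| Q1M | 0.1 | 10.26 | 0.977 | 1.018 |
| Q1M | 0.2 | 7.93 | 0.997 | 1.047 |
| Q1M | 0.3 | 6.45 | 0.998 | 1.079 |
| Q1M | 0.5 | 4.77 | 0.969 | 1.141 |
| Q1M | 0.8 | 3.51 | 0.920 | 1.230 |
| Q2M | 0.1 | 14.04 | 0.874 | 1.079 |
| Q2M | 0.2 | 9.68 | 0.967 | 1.206 |
| Q2M | 0.3 | 7.54 | 0.998 | 1.332 |
| Q2M | 0.5 | 5.39 | 0.982 | 1.580 |
| Q2M | 0.8 | 3.89 | 0.931 | 1.935 |

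Worked example, Q2M, ka = 0.8: C(0) = 1/0.8880 − 1 = 0.126; C(4 h) = 0.9939/0.8880 − 0.8752 = 0.244; ratio 1.94. Worked example, Q2M, ka = 0.1: C(7)/Cmax = 0.3746/0.4286 = 0.874.

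So true Tmax runs from 3.5 to 10.3 d (Q1M) or 3.9 to 14.0 d (Q2M), while the reported value stays at about 7 d. The day-7 value is 0 to 8% (Q1M) or 0 to 13% (Q2M) below Cmax; drawn at day 6, the worst Q2M case is 17% low (ratio 0.827). A draw 4 h after the dose overstates the trough by 2 to 23% (Q1M) or 8 to 94% (Q2M).

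**Step 4: is steady state the problem?** No. Month 6 is 180/19 = 9.5 half-lives after the first dose.

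**The case against.** The best defence has five parts.

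1. **Ctrough is obtainable.** The End of Treatment draw follows the last dose by about 30 or 60 days with no dose that day, so draw order cannot affect it. This stands. A reader might infer that the schedule cannot deliver any of the primary PK endpoints. It does not go that far: only Tmax is unobtainable, Cmax is approximated, and each child who reaches End of Treatment has at least one sound trough.

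2. **Mis-ordered draws can be found.** SAP Section 6 uses actual times for PK parameters, SAP 11.1 lists time from the previous injection and sends timing deviations to the pre-lock review meeting, and it presupposes pre-dose samples. The Laboratory Manual, not available here, may fix the order. This stands in part. But a same-day post-dose draw complies with the protocol, so it is not a deviation to be reviewed. Concentration summaries use planned time points, which would pool it with pre-dose values. Neither document says which samples define Ctrough.

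3. **The Day 1 PD baseline is protected.** One might extend the draw-order worry to the Day 1 PD and antibody samples. The first dose must be given on site, so the home-dosing route does not apply, and SAP 7.2.3 already restricts baseline to values before the first dose. The antibody summary in SAP 10.2.3 is by visit and not relative to baseline. No further exclusion is needed.

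4. **The magnitudes are assumed.** True. They rest on an adult half-life and a chosen absorption range, and nothing shows how often post-dose trough draws would occur. The 6-to-8-day Tmax window needs neither assumption.

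5. **Sparse sampling is deliberate.** Blood-volume caps of 61 and 65 mL (Protocol Section 8) limit extra draws. That explains the schedule; it does not make noncompartmental Tmax informative.

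**Conclusion.** The point holds for Tmax by inspection of the schedule: a primary endpoint would be reported that carries essentially no information about the drug. It would be wrong to say that the value is always 6 to 8 days, since a Q1M child with slow absorption can return 0.

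For Cmax the issue is mainly one of labelling. The bias is downward and modest, about 0 to 13% for a day-7 draw, given ka of 0.1 to 0.8 per day and a 19-day half-life.

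For Ctrough the gap is a missing rule rather than a demonstrated error. It matters little in Q1M if absorption is slow and potentially a great deal in Q2M if absorption is fast (up to 94% at 4 h under the same assumptions). It is confined to dosing-day draws after the first dose.

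The study is descriptive, so no test or error rate is affected.

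**What to change.** 1. In Protocol 9.4.4.1 and SAP 11.2, drop noncompartmental Tmax and report the +7-day value as the concentration about 7 days post-dose. Take steady-state Cmax and Tmax from the population PK model already planned, labelled as model-based.
2. In Protocol 1.3.1 footnote J and 1.3.2 footnote K, state that PK/PD draws on dosing days are taken before that day's dose.
3. In the SAP, name the samples that define Ctrough (pre-dose dosing-day draws and End of Treatment), and exclude from Ctrough any draw timed after that day's dose.
4. Reconcile the every-dose wording in footnotes J and K with the single column in Section 1.3.3.

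Cost: no extra blood. Because the stated method for a primary endpoint changes, the protocol needs amending as well as the SAP, and the SAP must link to the modelling plan's output. The drawback is that Cmax and Tmax become model-dependent. With such sparse data the individual Tmax will lean on the model's absorption assumptions, which should be said wherever it is reported. The modelling plan is not among the documents, so its adequacy for this purpose needs checking first.

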#### **9.4.5. Pharmacodynamic Analyses**

PD data will be summarized using the PD Analysis Set. FXIIa-mediated kallikrein activity and FXII concentration will be listed by individual subjects and will be summarized by nominal time point and dosing regimen (ie, 100 mg Q2M, 100 mg Q1M). The PD data will be summarized with descriptive statistics: n, number and percentage of values below the limit of quantification, mean, SD, CV%, median, minimum, maximum, first and third quartiles for continuous variables, geometric mean and its respective 90% CI, and geometric CV%.

Additional information on the analyses of PD will be provided in the SAP.

#### **9.4.6. Multiple Comparisons and Multiplicity**

Type I error rate adjustment is not applicable, as there is no confirmatory test planned in this study. No statistical tests are planned.

#### **9.4.7. Missing Data and Imputation**

Missing efficacy data will not be imputed, as there is no formal statistical analysis being done. All subjects who drop out within the first 30 days of the Treatment Period will be regarded as missing for all efficacy analysis.

There will be no imputation of partial or complete missing dates.

Where AE start dates and / or times are missing or partially missing, AEs will be assumed to be treatment-emergent, except if the partial start dates and / or times or the AE end date and / or time indicate that the AE started before the first administration of study treatment.

If for a TEAE the relationship to study treatment is missing, the worst case will be assumed for summarizing analysis (ie, the relationship to study treatment will be assumed to be “Yes”). If the AE or SAE with missing relationship started before the first injection of study treatment, it will be considered as “not related” (realistic case). No other imputations for missing AE information will be done.

### **9.5. Interim Analysis**

No formal interim analyses or sample size re-estimation are planned for this study.

## **10. SUPPORTING DOCUMENTATION AND OPERATIONAL CONSIDERATIONS**

### **10.1. Regulatory, Ethical, and Study Oversight Considerations**

#### **10.1.1. Clinical Trial Research Agreement**

This study will be conducted under a Clinical Trial Research Agreement between the sponsor and the institution(s) representing the investigational study site(s). Financial support to the investigational site(s) will be detailed in the Clinical Trial Research Agreement. The Clinical Trial Research Agreement must be signed before the commencement of the study and will clearly delineate the responsibilities and obligations of investigator and sponsor and will form the contractual basis under which the clinical study will be conducted. Clinical Trial Research Agreements may be executed by electronic signature (current provider DocuSign) in compliance with 21 Code of Federal Regulations (CFR) Part 11 and simple or advanced electronic signature according to European Union (EU) Regulation No 910/2014 - eIDAS.

#### **10.1.2. Regulatory and Ethics Considerations**

This study will be conducted in accordance with the CSP and with the following:

- Consensus ethical principles derived from international guidelines including the Declaration of Helsinki
- Applicable ICH GCP guidelines
- Applicable laws and regulations such as EU Clinical Trials Regulation 536/2014

The CSP, CSP amendments, ICF, Investigator's Brochure, and other relevant documents (eg, advertisements, study manual, and patient / caregiver facing materials) must be submitted to an IRB / Independent Ethics Committee (IEC) by the investigator and reviewed and approved by the IRB / IEC before the study is initiated.

Any CSP amendments will require IRB / IEC approval before implementation of changes made to the study design, except for changes necessary to eliminate an immediate hazard to study subjects.

CSPs and CSP amendments will require health authority approval prior to initiation except for changes necessary to eliminate an immediate hazard to study subjects.

The investigator will be responsible for the following:

- Providing written summaries of the status of the study to the IRB / IEC annually or more frequently in accordance with the requirements, policies, and procedures established by the IRB / IEC.
- Notifying the IRB / IEC of SAEs or other significant safety findings as required by IRB / IEC procedures.
- Providing oversight of the conduct of the study at the site and adherence to requirements of 21 CFR, ICH guidelines, the IRB / IEC, European Clinical Trials Regulation 536/2014 for clinical studies (if applicable), European Medical Device Regulation 2017/745 for clinical device research (if applicable), and all other applicable local regulations.

**10.1.3. Financial Disclosure**

Details regarding financial disclosure are provided in the Clinical Trial Research Agreement and ICF for the study.

**10.1.4. Informed Consent Process**

- The investigator or delegate will explain the nature of the study to the subject or their legally authorized representative and answer all questions regarding the study.
- Subjects must be informed that their participation is voluntary. Subjects or their legally authorized representative will be required to sign a statement of informed consent that meets the applicable requirements of 21 CFR 50, local regulations, ICH guidelines, Health Insurance Portability and Accountability Act requirements, and the IRB / IEC or study site.
- The medical record must include a statement that written informed consent was obtained before the subject was enrolled in the study and the date the written consent was obtained. The authorized person obtaining the informed consent must also sign the ICF.
- Subjects must be reconsented to the most current version of the ICF(s) during their participation in the study.
- A copy of the ICF(s) must be provided to the subject or their legally authorized representative.
- A subject who is rescreened is not required to sign another ICF.

